9.4.3.1 Adverse Events

Adverse events will be coded using the most recent version of the MedDRA.

Adverse events will be presented separate for each Part by treatment, SOC and/or PT presenting number and percentage of participants reporting at least one event. Number of events will be presented separately.

Only AEs occurring with an onset date, or worsening, on or after first dose of study intervention will be presented in summary tables. Adverse events occurring prior the first dose of study intervention will be included in data listings.

An overview of AEs will be presented for each Part and treatment. The presentation will include the number and percentage of participants with any AE, AEs with outcome of death, SAEs, AEs leading to discontinuation of study intervention, AEs leading to withdrawal from study, and AEs of special interest (including infection, eosinophilia, and hypersensitivity events) as well as the number of individual occurrences in those categories.

An additional table will present the number and percentage of participants with most common AEs. Most common (eg, frequency of >5%) will be defined in the SAP.

In accordance with the requirements of the FDA, a separate table will present non-serious AEs occurring in more than 5% of participants in any treatment group.

Key participant information will be presented for participants with SAEs with outcome of death, SAEs, and AEs leading to discontinuation of study intervention.

An AE listing for the SS will cover details for each individual AE; an AE listing for participants who were not exposed to study intervention will be presented separately.

Full details of the AE analyses will be provided in the SAP.

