Final 5.0	Last Signature	SAP updated for anticipated closure to remove some of the exploratory endpoints, the Per Protocol analysis and subgroup analysis. In addition the AE tables were presented for all the AEs after IP and by ADA status. The table including the number and percentage of subjects with a change from baseline in hsCRP higher than 5 and 10 mg/dL by ADA category and the Figure for hsCRP by week by ADA status and by treatment group will be also presented.

LIST OF ABBREVIATIONS

Abbreviation/Acronym	Definition/Expansion
ACQ-6	Asthma Control Questionnaire-6
ADA	Anti-drug antibody
AE	Adverse event
AESI	Adverse event of special interest
ALT	Alanine aminotransferase/transaminase
ANCOVA	Analysis of covariance
AST	Aspartate aminotransferase/transaminase
ATC	Anatomical therapeutic chemical
AUClast	Area under the serum concentration-curve from zero to the last quantifiable concentration
AUC τ	Area under serum concentration-time curve in the dosing interval
BDRM	Blind data review meeting
BID	Bis in die (twice daily)
BLQ	Below the lower limit of quantification
BMI	Body Mass Index
BP	Blood pressure
CI	Confidence interval
CL/F	Apparent total body clearance of drug from serum after extravascular administration
CRF	Case Report Form
CRP	C-reactive protein
CSP	Clinical study protocol
CSR	Clinical study report
Cmax	Maximum observed (peak) serum concentration
CS	Clinically significant
Ctrough	Concentration immediately prior to dosing
CV	Coefficient of variation
DBP	Diastolic blood pressure

Abbreviation/Acronym	Definition/Expansion
DPI	Dry powder inhaler
DRM	Data Review Meeting
DSMB	Data Safety Monitoring Board
ECG	Electrocardiogram
eCRF	electronic Case Report Form
EN	Enrolled analysis set
FAS	Full analysis set
FDA	Food and Drug Administration
FeNO	Fractional exhaled nitric oxide
FEV ₁	Forced expiratory volume in 1 second
FSH	Follicle stimulating hormone
FVC	Forced vital capacity
GeoCV	Geometric coefficient of variation
GeoLSMeans	Geometric LS means
gSD	Geometric SD
CCI	CCI
HR	Heart rate
ICF	Informed consent form
ICH	International Council for Harmonisation
ICS	Inhaled corticosteroids
IgE	Immunoglobulin E
IL	Interleukin
IP	Investigational Product
IPD	Important protocol deviations
IS	Immunogenicity set
LABA	Long-acting beta-adrenoceptor agonists
LLOQ	Lower limit of quantification
LOCF	Last observation carried forward
MedDRA	Medical Dictionary for Regulatory Activities

Abbreviation/Acronym	Definition/Expansion
MMRM	Mixed model repeated measure
NA	Not applicable

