4.17.1 Adverse Events/Serious Adverse Events

Adverse events will be coded using MedDRA latest available version.

All reported AEs will be listed along with the date of onset, date of resolution (if AE is resolved), investigator's assessment of intensity, outcome, action taken with IP, and possible relationship to study drug (assessed by investigator). A by subject listing of all AE (including AEs before first dose of study medication) will be provided. This listing will include the following information: study period, verbatim term, MedDRA SOC, and preferred term, start date/time, end date/time, time from last dose, intensity, causality, action taken, whether the AE was classified as serious, the outcome of the AE and the concomitant or additional treatment given, if any. Any AE occurring before the first dose of IP and/or the AE assessments that are unresolved at the participant's last assessment in the study will be included in the data listings but will not be included in the summary tables of AEs.

Multiple occurrences of an AE in the same subject will only be counted once overall considering start date as the first day of first occurrence and stop date the last day of the last occurrence and the AE will assigned to the treatment of the first occurrence period study drug. Multiple occurrences of an AE in the same subject for the same treatment will only be counted once for that treatment.

Statistical Analysis Plan

The number of subjects will be tabulated also by SOC, preferred term, and treatment.

In the case that, during the study, a subject has more than 1 episode of the same preferred term with different levels of intensity, action taken, outcome causality or seriousness, then the maximum intensity level, action taken (ie, withdrawn) and outcome (ie, fatal), causality level (ie, related), or seriousness level (ie, serious), respectively will be used.

The following ordering will be used to define maximum intensity level, action taken, outcome causality level, or seriousness level:

- Intensity: Mild < Moderate < Severe
- Causality: No < Yes
- Seriousness: No < Yes
- Action taken: Unknown < Not applicable < Dose not changed < Drug interrupted < Drug withdrawn
- Outcome: Unknown < Recovered/resolved < Recovered/resolved with sequelae < Recovering/ resolving < Not recovered/not resolved < Fatal

A general summary of all AEs will show the number and percentage of subjects with:

- Any AE
- Any SAE
- Any SAE with outcome death

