- SOC and preferred term.
- SOC, preferred term, and maximum intensity.
- SOC, preferred term, and relationship to study intervention judged by investigator.

Adverse event summaries will be ordered in terms of decreasing frequency for SOC, and preferred term within SOC.

The tables of AE will include all the AEs with an onset date and time on or after the date and time of first dose of IP up to the end of treatment + 96 hours. Additional tables including all the AEs experienced after the IP until last follow-up (Day 56) and for ADA status will be reported for both Part 1 and Part 2.

Adverse events sorted by decreasing frequency and AEs leading to discontinuation of investigational product by SOC and preferred term will be summarised.

The number and percentage of subjects who experience 1 or more SAEs will be tabulated by treatment group (AZD1402 and placebo) and by SOC and preferred term and by SOC and preferred term and with outcome of death.

For each subject and each AE, the worst severity recorded will be attributed and used in the by-severity summaries. Similarly, the worst causality (most related to treatment) will be attributed and used in the by-causality summaries. If severity or causality is missing, a conservative approach for AE assessment (taking into account the worst case) will be followed.

Key subject information for participants experiencing SAE with outcome death, SAEs, and AEs leading to discontinuation of IP will be presented in a listing. All the AE will be included in the data listings.

Statistical Analysis Plan

For AEs with partial dates/times, worst case is always assumed; if possibly on-treatment, then on-treatment is assumed, on-treatment AEs will be considered to have the longest possible duration and off-treatment AEs will be considered to have the shortest possible duration. In accordance with this principle, any AEs with incomplete start and end dates/times will be treated as follows:

- AEs with unknown start times, but with start date known, will be imputed with a time of 00:00, unless the start date corresponds to any given dosing date. In this case the start time will be imputed with the time of dosing. If this results in a start date/time after end date/time of the AE, then the time will also be imputed with 00:00.

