4.20 Change in the Conduct of the Study or Planned Analysis

SAP updated for anticipated closure to remove some of the exploratory endpoints, the Per Protocol analysis and subgroup analysis.

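### SAP 4.17.1 both excludes and includes adverse events still unresolved at a participant's last assessment in the AE summary tables

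*SAP*

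**What the plan says.** SAP 4.17.1 first names what stays out of the AE tables. The sentence opens with two classes of event, the second tied to a participant's final assessment: "Any AE occurring before the first dose of IP and/or the AE assessments that are unresolved at the". The two classes are joined by and/or, so the exclusion covers more than pre-dose events. The sentence closes with what happens to them: "last assessment in the study will be included in the data listings but will not be included in the summary tables of AEs".

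Further on, the same section defines the tables by onset: "The tables of AE will include all the AEs with an onset date and time on or after" first dose, up to end of treatment plus 96 hours. It then adds a second set: "Additional tables including all the AEs experienced after the IP until last follow-up (Day 56"), with tables by ADA status. Neither sentence mentions resolution. The Final 5.0 entry in the SAP revision history describes the change in the same inclusive terms: "In addition the AE tables were presented for all the AEs after IP and by ADA status".

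Protocol 9.4.3.1 also works from onset: "Only AEs occurring with an onset date, or worsening, on or after first dose of study intervention will be presented in summary tables". Only pre-dose events are assigned to listings there. Of the AE overview it says: "The presentation will include the number and percentage of participants with any AE". It leaves full AE detail to the SAP.

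SAP 4.20 declares the changes to the planned analysis: "SAP updated for anticipated closure to remove some of the exploratory endpoints, the Per Protocol analysis and subgroup analysis". Dropping unresolved AEs is not among them.

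On the secondary point, SAP 4.17.2 and the Final 5.0 revision entry set the hsCRP change-from-baseline cut-offs by ADA status at 5 and 10 mg/dL. SAP 4.6 lists hsCRP in mg/L. The CRP thresholds in SAP 3.2.2.1 and Protocol 5.1.3, 5.1.4, 7.1.2 and 8.3.5 are also in mg/L.

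**The concern.** AEs are part of the primary safety endpoint in Part 1 and a secondary endpoint in Part 2. A filter on resolution removes events by persistence. Late-onset events are also more exposed to it, because they have less time to resolve before the last visit; that bears on the Day 56 tables.

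The clearest case is a participant who withdraws because of an AE. Under Protocol 7.2 the last assessment is then normally the early termination visit, where the causative event may well still be open. The row for AEs leading to study withdrawal could then miss the event it exists to count. Later resolution would not restore it, because Protocol 8.3.2 has unresolved events followed without further eCRF entry.

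For hsCRP, 5 and 10 are the same numbers that serve elsewhere as CRP thresholds in mg/L. A tenfold unit slip would leave the one categorical table by ADA status unable to register moderate rises.

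**Working it through.** There is no figure in the plan to reproduce. The main check sets the rules side by side for one test event: onset during treatment, still open at the participant's last assessment.

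| Source | Criterion for the tables | Test event |
|---|---|---|
| SAP 4.17.1, exclusion sentence | not pre-dose and not unresolved at last assessment | out |
| SAP 4.17.1, main AE tables | onset from first dose to end of treatment + 96 h | in |
| SAP 4.17.1, additional tables | after first dose to Day 56 | in |
| SAP revision history, Final 5.0 | all AEs after study drug | in |
| Protocol 9.4.3.1 | onset or worsening on or after first dose | in |

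**Which rule was meant.** The exclusion stands alone. In the same section, the rule for choosing a participant's worst outcome over repeated episodes ranks the not-recovered category second only to fatal, which has little use if unresolved events never reach the tables. The section also takes the worst case for partially dated events. Protocol 8.3.2 speaks of events unresolved at the last assessment, but about follow-up and not tabulation. A transfer of that wording into the wrong place is plausible; this is inference.

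**Size of each step in the any-AE row.** Inputs are the planned sizes in SAP 3.1.1 and 3.1.2, with columns by Part for each dose, pooled AZD1402 and placebo (SAP 4.2, 4.17 and 4.17.1). I assume that all planned participants are treated and that Part 1 has a single placebo column. The step per participant whose only tabulated AE is dropped is 100/n percentage points.

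- Part 1a: 30 at 1:1:1 gives 30/3 = 10 per arm. Part 1b: 15 at 2:1 gives 10 active and 5 placebo.
- Part 1 dose column: 100/10 = 10 points.
- Part 1 placebo: 10 + 5 = 15; 100/15 = 6.7 points.
- Part 1 pooled AZD1402: 10 + 10 + 10 = 30; 100/30 = 3.3 points.
- Part 2, arm of 80: 100/80 = 1.25 points.
- Part 2, arm of 5: 100/5 = 20 points.
- Part 2 pooled AZD1402: 80 + 5 = 85; 100/85 = 1.2 points.

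A participant with another, resolved AE still counts in this row, though not under the lost preferred term.

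**hsCRP units.** 1 mg/dL = 10 mg/L, so 5 and 10 mg/dL are 50 and 100 mg/L. The level needed to pass a cut-off is baseline plus cut-off. I assume that baseline hsCRP lies under the CRP entry limits (below 5 mg/L in Part 1, Protocol 5.1.3; below 10 mg/L in Part 2, Protocol 5.1.4).

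- Part 1: lower cut-off 0 + 50 = 50 up to 5 + 50 = 55 mg/L; upper cut-off 100 to 105 mg/L.
- Part 2: lower cut-off 0 + 50 = 50 up to 10 + 50 = 60 mg/L; upper cut-off 100 to 110 mg/L.

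**The case against.** The best reply is that the intended rule is not really in doubt. The inclusive sentence is the specific tabulation rule, the outcome ranking and the protocol agree with it, and the exclusion is one garbled clause. SAP 4.2 also leaves remaining programming detail to the table shells, which are not part of these documents and may show no resolution filter. All AEs stay in the listings, and serious AEs and those leading to discontinuation of study drug also have a key-information listing. Protocol 9.4.3.1 delegates detail to the SAP, so the clause narrows the protocol without flatly contradicting it.

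Most of this is right on intent and on the limits of the harm. It does not cure the text. A specific exclusion beside a general inclusion is naturally read as an exception, so a careful programmer could apply it. Listings do not replace incidence tables. The point-per-participant figures are only 1/n, and the 20-point step reflects a five-person arm; they give scale and do not estimate the loss.

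Two further objections stand. Removing the clause does not bring in the protocol's provision for pre-dose events that worsen on treatment, because the SAP tables would still go by onset alone. And the hsCRP unit is not shown to be wrong: both places that describe the table use mg/dL, and cut-offs of 50 and 100 mg/L could be deliberate. If 5 and 10 were applied to values held in mg/L, the fault would be only a label. SAP 4.17.2 standardises units and reports in SI units in the CSR, which may expose the mismatch but does not state the intended cut-offs.

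**Conclusion.** The contradiction is real, and the exclusion is wrong as written. It would remove persistent treatment-emergent events from the tables of a primary safety endpoint, has no basis in Protocol 9.4.3.1 and is not declared in SAP 4.20. Confidence in the textual conflict is high.

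The total effect is unknown because the documents give no share of unresolved events. It runs from zero, if the onset rule is programmed, upwards in the steps shown above for each participant whose only tabulated AE is lost. Actual columns may be smaller than planned, and the steps larger, since Final 5.0 was written for anticipated closure.

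The hsCRP point is minor and needs confirmation only. If the cut-offs are converted and applied as 50 and 100 mg/L, the categorical table will not register rises of 50 mg/L or less. The hsCRP figure by ADA status and the CRP shift tables and plots are unaffected.

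**What to change.** In SAP 4.17.1, delete the part of the exclusion sentence that refers to AE assessments unresolved at the last assessment. Pre-dose events then remain the only listing-only class in that sentence, and the tables follow the onset windows whatever the resolution status. While editing, it would be sensible to state how pre-dose events that worsen on treatment are handled, since Protocol 9.4.3.1 includes them.

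Separately, confirm the hsCRP unit and restate the cut-offs in mg/L in SAP 4.17.2, or justify mg/dL if it was intended. The revision history describes the same table and should agree, but 4.17.2 is the operative text.

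Deleting the AE clause costs one wording change and at most one table filter. The hsCRP point costs one wording change and at most one table threshold. Neither needs new data.

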3 OBJECTIVES AND ENDPOINTS

Table 3 Objectives and Endpoints (Part 1)

Objectives	Outcome Measure
Primary	

 To evaluate the safety and tolerability of AZD1402 compared to placebo at different dose levels in adults with asthma controlled on medium dose ICS-LABA 	
Primary safety endpoint:
 
 Adverse events / AESIs / SAEs with a particular focus on infection, eosinophilia, and hypersensitivity-like events Vital signs Changes in clinical chemistry, haematology, and coagulation parameters Immuno-biomarkers (including but not limited to cytokines, CRP, immunoglobulins including IgE) ECGs FEV₁ FeNO
Secondary	

 To investigate the PK profile and immunogenicity of AZD1402, and associated effects on safety 	
 PK parameters (full profile in all participants) ADAs
Exploratory	

 CCl [REDACTED] 	
 Change from baseline in FeNO at Day 28 and average over the Treatment Period CCl [REDACTED]

 To assess the effect of AZD1402 compared to placebo on cough by a VAS in adults with asthma controlled on medium dose ICS-LABA 	
 Change from baseline average in cough VAS over the Treatment Period

 CCl [REDACTED] 	
 CCl [REDACTED] CCl [REDACTED]

 CCl [REDACTED] 	
 CCl [REDACTED] CCl [REDACTED]

Table 3 Objectives and Endpoints (Part 1)

Objectives	Outcome Measure

 • CCI 	
 • CCI • CCI

Abbreviations: CCI [REDACTED] ADAs = anti-drug antibodies; AESI = adverse event of special interest; CSR = clinical study report; CRP = C-reactive protein; ECG = electrocardiogram; FeNO = fractional exhaled nitric oxide; FEV₁ = forced expiratory volume in 1 second; CCI [REDACTED] ICS = inhaled corticosteroids; IgE = immunoglobulin E; LABA = long-acting beta agonist; CCI [REDACTED] PK = pharmacokinetics; SAEs = serious adverse events; VAS = Visual Analogue Scale

Table 4 Objectives and Endpoints (Part 2)

Objectives	Outcome Measure
Primary	

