
 • To investigate the efficacy of inhaled AZD1402 compared to placebo in adults with asthma who are uncontrolled on medium-to-high dose ICS-LABA 	
Primary efficacy endpoint:
 
 • Change from baseline in pre-bronchodilator FEV₁ at Week 4
Secondary	

 • To further investigate the efficacy of AZD1402 compared to placebo in adults with asthma who are uncontrolled on medium-to-high dose ICS-LABA 	
 • Change from baseline in pre-bronchodilator FEV₁ average over the 4-week Treatment Period • Change from baseline in ACQ-6 at Week 4 and average over the Treatment Period • Proportion of participants with a decrease in ACQ-6 score of ≥ 0.5 from baseline to Week 4 • Change from baseline in average morning PEF over the Treatment Period • Change from baseline in average evening PEF over the Treatment Period • Change from baseline in daily average asthma symptom score (AM/PM) over the Treatment Period

 • To investigate the effect of AZD1402 compared to placebo on airway inflammation in adults with asthma who are uncontrolled on medium-to-high dose ICS-LABA 	
 • Change from baseline in FeNO (in-clinic) at Week 4 and average over the Treatment Period

 • To investigate the PK profile and immunogenicity of AZD1402, and associated effects on safety 	
 • PK parameters (sparse in all, full profile in a subset of participants in each treatment arm) • ADAs

 • To evaluate the safety and tolerability of AZD1402 compared to placebo in adults with asthma who are uncontrolled on medium-to-high dose ICS-LABA 	
 • Adverse events / AESIs / SAEs with a particular focus on infection, eosinophilia, and hypersensitivity-like events • Vital signs

Table 4 Objectives and Endpoints (Part 2)

Objectives	Outcome Measure
	
 Changes in clinical chemistry, haematology, and coagulation parameters Immuno-biomarkers (including but not limited to cytokines, CRP, immunoglobulins including IgE) ECGs FEV₁ FeNO
Exploratory	

 CC1 [REDACTED] 	
 CC1 [REDACTED] CC1 [REDACTED] CC1 [REDACTED] CC1 [REDACTED] CC1 [REDACTED] CC1 [REDACTED] Change from baseline in FeNO

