4.4.1 Premature Termination of the Study and Stopping Criteria

The Sponsor will suspend or terminate a dose level or the entire study (as applicable) following the review of all available safety data if any of the following occurs at the dose or study level:

Per dose level (Part 1)

- Two participants experience a FEV₁ drop $\geq 30\%$ from baseline (in-clinic)* attributable to AZD1402.
- One participant experiences a hypersensitivity-like SAE attributable to AZD1402.

- Day 28 exposure in one participant in Part 1 exceeds or is predicted to exceed (for Part 1b) a peak concentration Cmax of 5420 ng/mL or exposure AUC(0-24 h) of 68700 ng.h/mL.

*Baseline Part 1: Mean of Day -1 and Day 1.

Per dose level (Part 2)

- Clinically significant FEV₁ decline from baseline* attributable to AZD1402 comparing the number of participants reaching a FEV₁ drop $\geq 30\%$ in active versus placebo as assessed by the DSMB.
- One participant experiences a hypersensitivity-like SAE attributable to AZD1402.

*Baseline Part 2: Mean of Day 1 (15 minutes and 45 minutes pre-dose).

Study level

- Two participants experience a hypersensitivity-like SAE and/or severe hypersensitivity event attributable to AZD1402.
- The overall safety and tolerability profile as determined by the DSMB does not justify continuation with dosing as per the current protocol.
- Significant immunogenicity impacting safety and tolerability.
- The Sponsor considers the applied doses of the study intervention to be no longer relevant.
- The Sponsor decides to discontinue the study.
- Data not known before, become available and raise concern about the safety of AZD1402 so that continuation would pose potential risks to the participants.

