8.3.5 Adverse Events of Special Interest

The following events (occurring after first dose) will be considered to qualify as an AESI for this study.

- $FEV_1 \geq 20\%$ reduction from baseline as informed by in-clinic assessment ("forced expiratory volume decreased")
- $FEV_1 \geq 30\%$ reduction from baseline as informed by
 - in-clinic assessment
 - decline is sustained over 2 scheduled consecutive home assessments resulting in either dosing suspension or discontinuation (Part 2)
- Confirmed fever ($> 38^\circ\text{C}$ for > 4 hours)
- Wheeze*
- Cough*
- Dyspnoea/shortness of breath*
- Infection
 - respiratory tract infection, ideally supported by pathogen identification and confirmation
 - COVID-19 infection.
 - non-respiratory tract infection

* Part 1: All new events of wheeze, cough, dyspnoea/shortness of breath.

Part 2: All new worsening events of wheeze, cough, dyspnoea/shortness of breath compared to baseline / individual pre-existing disease characteristics as judged by the Investigator.

In the event of suspected respiratory infection, pathogen identification include:

- SARS-CoV-2 PCR.
- Viral panel which may include, but are not limited to influenza (all types), parainfluenza, respiratory syncytial virus, human metapneumovirus, adenovirus and *Bordetella pertussis*.
- *Mycoplasma pneumoniae* and *Chlamydophila pneumoniae* (sometimes included in viral panel).
- Bacterial swab to detect any growth which may include, but are not limited to *Streptococcus*, *Klebsiella*, *Pneumoniae*, *Pseudomonas*, *Staphylococcus aureus*, *E.coli*, *Citrobacter*, *Acinetobacter* and *Haemophilus influenzae*.

The pathogen identification may be performed locally in the first instance, in which case the available tests may differ from those listed. In the event that local laboratory is not used, it may be performed centrally as per standard panel agreed with the Sponsor.

Additionally, CRP ≥ 10 mg/L should be used to support the evaluation and identification of the potential cause of an AESI and to guide further dosing. Unscheduled visit including blood samples collection (including but not limited by haematology, CRP, immuno-biomarkers), local CRP, spirometry, throat swab for pathogen identification, and any other relevant tests which might be required for AE assessment may be requested and scheduled.

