- Any AE leading to discontinuation of IP
- Any AE leading to withdrawal from study

An overview summary of AEs together with a presentation of AEs (event count) by preferred terms and sorted by decreasing frequency on preferred term will be also produced. In addition, an overview summary of the number and percentage of subjects with AEs and by SOC, preferred term, and treatment will be also presented by ADA status.

Additional tables will present the number and percentage of subjects with any AESI occurring after first dose (including infection, eosinophilia, and hypersensitivity events) and the in-clinic alerts with the individual occurrences in those categories.

The AESI presented in the table will be (for in-clinic assessments):

- FEV₁ drop $\geq 20\%$ reduction from baseline as informed by in-clinic assessment: information extracted from the AE page on the eCRF.
- FEV₁ drop $\geq 30\%$ reduction from baseline as informed by:
 - in-clinic assessment.
 - decline is sustained over 2 scheduled consecutive home assessments resulting in either dosing suspension or discontinuation (Part 2).
- Confirmed fever ($> 38^{\circ}\text{C}$ for > 4 hours)
- Wheeze*
- Cough*
- Dyspnoea/shortness of breath*

Statistical Analysis Plan

- Infection
 - respiratory tract infection, ideally supported by pathogen identification and confirmation.
 - COVID-19 infection.
 - non-respiratory tract infection.

*Part 1: All new events of wheeze, cough, dyspnoea/shortness of breath.

Part 2: All new worsening events of wheeze, cough, dyspnoea/shortness of breath compared to baseline / individual pre-existing disease characteristics as judged by the Investigator.

In the event of suspected respiratory infection, pathogen identification include:

- SARS-CoV-2 PCR.
- Viral panel which may include but are not limited to influenza (all types), parainfluenza, respiratory syncytial virus, human metapneumovirus, adenovirus, and *Bordetella pertussis*.
- *Mycoplasma pneumonia* and *Chlamydophila pneumoniae* (sometimes included in viral panel).
- Bacterial swab to detect any growth which may include, but are not limited to *Streptococcus*, *Klebsiella*, *Pneumoniae*, *Pseudomonas*, *Staphylococcus aureus*, *E. Escherichia coli*, *Citrobacter*, *Acinetobacter* and *Haemophilus influenza*.

The number and percentage of subjects who experience one or more AEs will be tabulated by each study part, treatment group (dose level of AZD1402, pooled AZD1402, and placebo) and by:

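### Eosinophilia and hypersensitivity are named as contents of the AESI tables, but no row or definition in the SAP or protocol allows either to be counted as a group

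*SAP*

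**What the plan says.** The Part 1 primary safety endpoint (protocol section 3, Table 3) covers AEs, AESIs and SAEs "with a particular focus on infection, eosinophilia, and hypersensitivity-like events". The Part 2 secondary safety endpoint (Table 4) repeats this: "Adverse events / AESIs / SAEs with a particular focus on infection, eosinophilia, and hypersensitivity-like events".

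SAP 4.17.1 turns this into output. It states: "Additional tables will present the number and percentage of subjects with any AESI occurring after first dose", and adds in parentheses "including infection, eosinophilia, and hypersensitivity events". The content is then fixed by a sentence that begins "The AESI presented in the table will be (for in-clinic assessments", followed by seven top-level items: FEV1 fall of at least 20%, FEV1 fall of at least 30%, confirmed fever, wheeze, cough, dyspnoea, and infection. Infection is split into three kinds, the first being "respiratory tract infection, ideally supported by pathogen identification and confirmation".

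The protocol is divided in the same way. Section 8.3.5 opens with "The following events (occurring after first dose) will be considered to qualify as an AESI for this study" and gives the same seven items. Section 9.4.3.1 says the AE overview will include AESIs, and describes these as including infection, eosinophilia and hypersensitivity.

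**The concern.** The sentence introducing the AESI tables and the list that follows it cannot both describe the same table. A programmer working from the list would produce infection and six respiratory or fever items, and nothing for eosinophilia or hypersensitivity. A programmer working from the sentence would have no rule for deciding which events belong in those two categories.

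The two categories matter to this trial. Protocol 2.3.1 reports hypersensitivity-like events in an earlier pharmacokinetic bridging study and says that the early observations altered the known risk profile. Protocol 4.4.1 has a dose-level stopping criterion that reads "One participant experiences a hypersensitivity-like SAE attributable to AZD1402", and a study-level criterion based on two participants. If the grouping is chosen only after results are seen, the choice of terms is open to influence from those results.

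**Working it through.** No figure in the plan needs to be reproduced. The check sets the relevant sections side by side.

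| Where | Infection | Eosinophilia | Hypersensitivity |
|---|---|---|---|
| Protocol section 3, safety endpoints, both parts | named | named | named |
| Protocol 9.4.3.1, AE overview | named | named | named |
| SAP 4.17.1, sentence introducing the AESI tables | named | named | named |
| Protocol 8.3.5, AESI definition | listed | not listed | not listed |
| SAP 4.17.1, items to be presented | listed | not listed | not listed |
| Term list, MedDRA grouping or count limit, either document | sub-types given | none | none |

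Three focuses are named and one has a row, so 2 of 3 have none.

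I then looked for any other output that could supply the grouped count.

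1. **General AE summary (SAP 4.17.1).** It covers any AE, SAEs, deaths, discontinuations and withdrawals. It has no AESI line, although protocol 9.4.3.1 puts AESIs in the overview.
2. **AE tables by system organ class and preferred term (SAP 4.17.1).** These include hypersensitivity and eosinophilia terms as reported. No rule gathers related terms into one category.
3. **Haematology (SAP 4.17.2).** Eosinophils are measured and summarised by treatment and time, out-of-range values are flagged in listings, and shift tables to the on-treatment maximum and minimum include all white cells. The treatment-emergent abnormality criteria cover only low leucocytes, neutrophils, platelets and lymphocytes. There is no high-eosinophil criterion.
4. **Eosinophilia as an AE term.** Under protocol 8.3.6 a laboratory deterioration is reported as an AE only if it is serious, leads to discontinuation or is judged clinically relevant. AE terms alone would therefore not capture every laboratory eosinophilia.
5. **Hypersensitivity-like events as classified at site.** Protocol 7.1.1, 7.1.2.1 and 7.1.2.2 ask the investigator to consider or exclude such an event. The AE variables listed in protocol 8.3.2 include no field for that classification, and no table counts it.
6. **Protocol Appendix I.** As supplied, it gives only literature references. Even if a diagnostic scheme was lost in conversion, it would not by itself say which coded events enter a table.

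The group sizes explain why grouping is useful. Part 1a has 30 / 3 = 10 participants per arm. Part 1b has 15 × 2/3 = 10 active and 15 × 1/3 = 5 placebo. As a purely hypothetical illustration, three participants in an arm of 10 with three different hypersensitivity terms would show as three preferred-term rows of 1/10 = 10%. A grouped row would show 3/10 = 30%.

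**The case against.** The strongest reply is that the mismatch is one of wording and that the information largely appears elsewhere. Much of this stands.

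- **Eosinophils by arm.** High values would show in the summaries and shift tables of SAP 4.17.2. It would be wrong to infer that eosinophilia appears only as scattered preferred terms. These displays are nevertheless laboratory shifts, not a count of participants with an eosinophilia event.
- **Severe hypersensitivity.** Under protocol 7.1.1 an acute severe event leads to permanent discontinuation, so it would reach the discontinuation table and, if serious, the SAE table. Milder events would not.
- **Respiratory signs.** Dyspnoea, wheeze, cough, fever and FEV1 falls each have a row. They may be part of a hypersensitivity-like picture, but they are counted separately and no rule combines them.
- **Unseen table shells.** SAP 4.17.1 speaks of tables in the plural, heads the list as in-clinic, and SAP 4.2 leaves presentation detail to a shells document. A reader might infer that the two categories will never be counted. The documents do not support that. They show only that no row or definition is given.
- **Stopping decisions.** A reader might infer that the missing rows weaken the stopping rules or would conceal a cluster of cases. The documents do not support this either. Those decisions rest on safety review by the sponsor, the SRC and the DSMB, not on this report table, and system organ class rows would show some clustering.

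The contradiction between the sentence and the list, and the absence of any definition, remain.

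**Conclusion.** The point holds in limited form. The AESI summaries are described as including three categories. The listed rows and the AESI definition deliver one, and neither document says how the other two would be identified. No specified table gives a grouped count, by arm, of participants with eosinophilia or hypersensitivity, although both are named focuses of the Part 1 primary and Part 2 secondary safety endpoints. This is a conflict between a stated list and the plan's own endpoint, not only an omitted detail.

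The consequence is an incomplete and non-prespecified summary, not loss of data. That conclusion assumes that the table shells do not already hold the definitions, and that the shift tables classify eosinophils by reference range, which SAP 4.17.2 implies but does not spell out. The sponsor should correct it. It does not call into question the conduct of the trial or the primary efficacy analysis.

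**What to change.** In SAP 4.17.1, add two rows to the AESI tables, by part and by arm, showing participants and events.

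- **Hypersensitivity.** Use a pre-specified MedDRA term grouping. The endpoint concerns hypersensitivity-like events, so also state whether events that the investigator classed in that way are counted and where that classification is recorded.
- **Eosinophilia.** Use AE preferred terms plus a treatment-emergent eosinophil criterion defined relative to baseline. An absolute limit alone could count participants who were already above it: Part 2 requires at least 150 cells/µL at Screening, and the SAP has a baseline group of 300 cells/µL or more.

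State which follow-up window applies, since SAP 4.17.1 uses both end of treatment plus 96 hours and Day 56. Fix the definitions before database lock. Disclose that the SRC, which may include the sponsor study team, had already reviewed Part 1 data unblinded, so that the Part 1 definitions are not presented as blind to those data. Align protocol 8.3.5, protocol 9.4.3.1 and SAP 4.17.1, including the AESI line missing from the SAP's general AE summary.

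The cost is SAP wording and one extra grouped table. AE coding and eosinophil counts are already collected. The investigator classification is the one item that may not exist as a recorded field, which is why its source must be stated.
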